7. SUBJECT SELECTION

7.1. Description of Study Population

The target population is patients with locally advanced primary and recurrent colorectal cancer, with confirmed positive RAS mutation eligible for radical pelvic surgery at time of enrolment.

7.2. Number and Source of Subjects

In this study approximately 4-6 (Part I) and up to 10 patients (Part II) will be enrolled, divided into the two sequential parts of the study. Patients will only be allowed to participate in either Part I or Part II of the study. Part II will only start after Part I has been completed. As stated above the start of Part II of the study will depend upon the level of immune activation and the safety profile in Part I. Patients will be recruited at 3-5 sites. Potential patients will be identified when patients are diagnosed with locally advanced primary and recurrent colorectal cancer by referrals.

7.3. Inclusion Criteria

1. Patients with locally advanced primary and recurrent colorectal cancer (CRC) (histologically or cytologically confirmed adenocarcinoma), with a confirmed oncogenic KRAS exon 2, codon 12 or 13 mutations, eligible for radical pelvic surgery at time of enrolment.
2. Patient is ≥ 18 years of age and able to consent
3. Eastern Cooperative Oncology Group (ECOG) performance status (PS) of 0 or 1
4. Patient has adequate organ and bone marrow function within 28 days of study
 - a. Neutrophil count $>1.5 \times 10^9/L$
 - b. Platelets $>100 \times 10^9/L$
 - c. Hb $>90g/L$
 - d. Total bilirubin <1.5 upper limit of normal, ULN
 - e. ALT and AST $<3.0 \times ULN$
 - f. Serum creatinine $<3 \times ULN$ or Creatinine Clearance $\geq 30ml/min$ (Cockcroft-Gault or Nuclear GFR method)
 - g. PT and APTT $<1.3 \times ULN$
5. The patient is willing to provide study specific pre TG02-treatment biopsy of tumour mass and allow use of archival tumour biopsies. For patients where there are technical reasons a baseline biopsy cannot be performed but who fulfil all the other inclusion criteria, the investigator shall contact the medical monitor to discuss the possibility of including such patient.
6. The patient is willing and able to comply with the protocol, and agrees to return to the hospital for study visits and examinations
7. Men and women of childbearing potential must use adequate contraception to prevent pregnancy during the study. Adequate contraception is defined in the study as any medically recommended method (or combination of methods) as per standard of care. An adequate contraception includes hormonal contraception with implants or combined oral, transdermal or injectable contraceptives, certain intrauterine devices, bilateral tubal ligation, hysterectomy, or vasectomy of partner. A combination of male condom with either cap, diaphragm or sponge with spermicide are also considered acceptable.

For women of childbearing potential, a negative pregnancy test needs to be confirmed before inclusion.

8. The patient has been fully informed about the study and is willing to participate in the study, and has provided written informed consent form prior to any trial specific screening procedures.

7.4. Exclusion Criteria

1. The patient has previously received an anticancer vaccine or immune checkpoint inhibitor, or participated in a trial involving the use of an anticancer vaccine or immune checkpoint inhibitor
2. Patients where pre-surgery radiotherapy, chemotherapy or other anti-cancer therapy has not been completed ≥ 2 weeks prior to TG02-treatment.
3. The patient is receiving anti-cancer therapy for concurrent illness
4. The patient has had a prior different malignancy within the last 3 years (excluding adequately treated basal cell or squamous cell carcinoma of the skin cancer, or localised low grade tumours considered cured and not requiring systemic therapy)
5. The patient has uncontrolled or significant intercurrent or recent illness including:
 - a. auto-immune disorder or history of autoimmune disease requiring immunosuppressive treatment
 - b. cardiac disorder such as uncontrolled cardiac failure, unstable angina or non-ST segment elevation myocardial infarction (NSTEMI) or myocardial infarction, uncontrolled arrhythmia less than 3 months before screening
 - c. stroke or thromboembolic event within 3 months of study commencement
 - d. active or uncontrolled severe infection
 - e. history of solid organ transplantation or any condition requiring chronic treatment with corticosteroids or other immunosuppressive agents
 - f. active coagulopathy/bleeding diathesis
 - g. cirrhosis, chronic active or untreated persistent hepatitis
 - h. history of adverse reactions to peptide vaccines
6. The patient is pregnant or lactating.
7. Has received an investigational drug within 4 weeks prior to study drug administration, or unless other has been agreed with the medical monitor
8. Is currently receiving any agent with a known effect on the immune system, unless at dose levels that are not immunosuppressive (e.g. prednisone at 10 mg/day or less or as inhaled steroid at doses used for the treatment of asthma)
9. Known history of positive tests for HIV/AIDS
11. Are planned to receive yellow fever or other live (attenuated) vaccines during the course of study
12. For Part II – any contraindication to receiving pembrolizumab:
For the 50 mg lyophilized powder: Hypersensitivity to the active substance (pembrolizumab) or to any of the excipients; L-histidine, L-histidine hydrochloride monohydrate, Sucrose, Polysorbate 80
For the 100 mg concentrate: Hypersensitivity to the active substance (pembrolizumab) or to any of the excipients; L-histidine, Sucrose, Polysorbate 80.

7.5. Discontinuation Criteria

Patient Withdrawal

Single patient termination is by definition when the patient is withdrawn or when the patient has died or completed the study. The study termination page in the eCRF must be completed.

In accordance with the Declaration of Helsinki, each patient is free to withdraw from the study at any time without giving their reason(s).

The investigator also has the right to withdraw patients from the study in the event of:

- withdrawal of the patient's consent
- surgery does not proceed and the patient is unable or unwilling to provide a biopsy at the time of cancelled surgery
- occurrence of an exclusion criterion which is clinically relevant and affects the patient's safety, and discontinuation is considered necessary by the Investigators and/or Targovax.
- therapeutic failure requiring urgent additional medication (if applicable)
- occurrence of AEs, if discontinuation of trial medication is desired or considered necessary by the Investigator and/or patient (if applicable)
- intake of non-permitted concomitant medication where the predefined consequence is withdrawal from the trial
- patient non-compliance with study procedures/requirements
- major protocol violation which potentially impacts the study endpoints

Study Termination

The whole study may be discontinued at the discretion of the Investigator or Sponsor in the event of any of the following:

- Occurrence of AEs not seen previously which by virtue of their nature, severity and duration are considered to necessitate study termination; OR the unexpected incidence of known AEs
- Medical or ethical reasons affecting the continued performance of the study
- Difficulties in the recruitment of patients
- Cancellation of the drug development as such or for the given indication

7.6. Replacement Policy

If a patient during the treatment period before surgery is withdrawn, the patient will be considered to be replaced. All safety data collected will remain part of the safety analysis.

8. TRIAL TREATMENT(S) AND REGIMEN OF INVESTIGATIONAL MEDICINAL PRODUCTS

8.1. Identity of Investigational Medicinal Product(s) (IMPs)

The TG02-treatment (GM-CSF/TG02) is manufactured according to Good Manufacturing Practice (GMP) standard.

In Part I the IMPs consists of two different products in two separate vials, 1 vial containing TG02 and 1 vial containing GM-CSF. In Part II, in addition to TG02 and GM-CSF, a third IMP, pembrolizumab will be used.

TG02

TG02 is a sterile dry white solid powder consisting of the eight drug substance peptides in equal amounts (weight net peptide) (Baccinex SA, Courroux, Switzerland/Bachem Distribution Services, GmbH).

TG02 is produced by lyophilisation of a sterile aqueous solution of the drug substance peptides. No additional ingredients are present in the TG02 drug product. Each vial of TG02 contains 2.4 mg of the drug substance peptides.

TG02 is supplied as a single dose in 2 mL clear glass vials. All the primary packaging materials used are in conformance with the European Pharmacopoeia (EP) and US Pharmacopoeia (USP).

TG02 drug product is to be reconstituted in water for injection (WFI) before administration to the patient. Patient will receive TG02 at a dose of 0.80 mg/injection.

An accountability log will be kept to track the use of TG02.

GM-CSF (Immunomodulator)

GM-CSF in the form of lyophilised recombinant human GM-CSF expressed in E-coli (Amoytop Biotech Co, Ltd, Xiamen, China) is used as immunomodulatory.

GM-CSF is a sterile dry white solid powder consisting of human recombinant GM-CSF and the excipients mannitol, macrogol 4000, human albumin, dibasic sodium phosphate and monobasic potassium phosphate. Each vial of GM-CSF contains 100 µg (1.0x10⁶ IU) Molgramostim. GM-CSF is supplied in a 2 mL clear glass vial.

GM-CSF is to be reconstituted in water for injection (WFI) before administration to the patient.

An accountability log will be kept to track the use of GM-CSF.

Pembrolizumab (Only Part II):

A fixed dose of 200 mg pembrolizumab will be administered as an intravenous infusion. The product will be provided as a 50 mg lyophilized powder in a single-use vial for reconstitution in sterile water for injection, or as a vial of 4 mL of concentrate containing 100 mg. Pembrolizumab should be administered according to the latest version of the

Summary of Product Characteristics (SmPC), and dosed according to available guidelines for the use of this drug.

An accountability log will be kept to track the use of Pembrolizumab.

8.2. Dosing, Mode of Administration, Duration of Treatment

TG02 and GM-CSF will be given as intradermal injections by trained study staff authorized to do such procedures. Training of study staff will be performed by Sponsor before any patients are treated. In addition, the administration of TG02 and GM-CSF is described in the Study Drug Handling Plan (SDHP).

GM-CSF and TG02 are administered as 2 separate intradermal injections, 15 to 30 minutes apart, at the same site in the upper arm. In addition, TG02 will at certain time points be administered intradermally (without prior administration of GM-CSF) in the lower area of the contra lateral arm as DTH test.

The administration of GM-CSF (0.10 mL reconstituted GM-CSF) and TG02 (0.10 mL reconstituted TG02) has to be strictly intradermal. Utmost care has to be taken that no material is administered subcutaneously. When done correctly, a small bleb should appear following the injection. An injection that is too superficial will result in loss of volume from the injection site during injection or after withdrawal of the needle. The administration should be performed at the same site every time, if possible.

TG02: provided as a lyophilised solid powder for reconstitution in sterile water for injection to be given via intradermal injection.

TG02 given in the TG02-treatment will be administered in the upper arm at weeks 1, 2, 3, 4, and 6. If surgery is scheduled after week 10 one more TG02-treatment will be given in week 10. **TG02 is to be given 15-30 minutes after GM-CSF.**

TG02 will at certain time points (week 1, week 4, week 6, week 8 and possible week 10), be administered intradermally (without prior administration of GM-CSF) in the lower area of the contra lateral arm as a DTH test to evaluate the immunological response (see [Table 6-1](#)).

Where a DTH (TG02) injection is being performed the TG02 DTH dose should be administered **30 minutes** before the TG02-treatment and patients should be observed for at least 30 minutes after ALL TG02 treatments.

GM-CSF: provided as a lyophilised solid powder for reconstitution in sterile water for injection to be given via intradermal injection.

GM-CSF given in the TG02-treatment will be administered in the upper arm at weeks 1, 2, 3, 4, and 6. If surgery is scheduled after week 10 one more TG02-treatment will be given in week 10 (see [Table 6-1](#)).

In the TG02-treatment GM-CSF is to be given 15-30 minutes before TG02.

The drug handling of TG02-treatment will be described in a separate Study Drug Handling Plan.

Table 8-1: Treatment schedule

Time point	DTH test (TG02)	TG02-treatment (GM-CSF followed by TG02)	Pembrolizumab (Part II of the study)
Week 1	X	X	
Week 2		X	
Week 3		X	
Week 4	X	X	X
Week 6	X	X	X
Week 8	X*		X***
Week 10 (only if surgery is after week 10)	X**	X	X

*If surgery is scheduled to be done in week 8, DTH (TG02) injection to be done approximately 48 hours prior to surgery.

** Only to be taken for patients who have surgery at week 10 or later and had a negative outcome at week 8.

*** If surgery is taking place Day 51-63, pembrolizumab will be given at Day 50/Week 8.

Pembrolizumab: A fixed dose of 200 mg pembrolizumab will be administered as an intravenous infusion. Pembrolizumab should be administered according to the latest version of the Summary of Product Characteristics (SmPC), and dosed according to available guidelines for the use of this drug. Dependent on time of surgery, a patient will receive pembrolizumab 2 to 4 times throughout the treatment period.

All handling of the IMPs/drug products should be in compliance with normal handling of sterile products for injections.

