TG02-treatment and DTH testing will occur in an identical manner to that described for the Part I of the study. Pembrolizumab should be administered as described previously. During the course of the study, the patient can expect to receive 2-4 intravenous infusions; week 4, week 6, and week 8 if surgery takes place Day51-63/Week8-10, and week 10 if surgery is delayed after day 64/Week 10. The dosing regimen should be the same for all patients at all sites.

Baseline and screening assessments:

Demographic details, medical and medication history, physical examination, vital signs (blood pressure, heart rate, tympanic temperature, weight, height), 12-lead ECG, ECOG performance status, routine laboratory testing (haematology and clinical chemistry), PET-CT, tumour biopsy, collection of blood for immune activity (PBMCs, serum and whole blood) and CEA.

Efficacy assessments:

- TG02-specific DTH response
- Presence of TG02 specific T-cells
- Change in intra-tumoural lymphocytes

- Change in immunological and pathological markers in tumour tissue
- Changes in FDG PET-CT images e.g. change in standard uptake value (SUV)
- Changes in CEA from baseline throughout treatment
- Changes in circulating tumour cells and/or circulating tumour DNA
- Functionality of RAS mutation specific T cells in tumour tissue and peripheral blood

Safety assessments:

Safety will be assessed by incidence and severity of adverse events as per NCI Criteria for Adverse Events (CTCAE) (v4.03: June 14, 2010), and by changes from baseline in laboratory variables, physical examination, vital signs and ECOG performance status.

Statistics:

The results from this study will be presented using descriptive statistical methods. Data will be presented by time of measurement, e.g. at baseline, week 1, week 4, week 8 etc. In general, continuous variables will be described using standard summary statistics such as number of observations, mean value, standard deviation, minimum and maximum value, median, and first and third quartiles. Categorical variables will be summarised in frequency tables as counts and percentages. All individual data collected will be presented in data listings. Patients screened but not included in the study will not be presented in any tables or listings.

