The treatment period will be from Day 1 (Week 1) and up to surgery, which is planned for week 8 but can occur in a window up to week 14. The following assessments will be performed on Day 1, Day 8, Day 15, Day 22, Day 36, Day 50 and if surgery is after week 10 (Day 64):

- Vital signs (heart rate, blood pressure and tympanic body temperature) and ECOG performance status
- Concomitant medications and adverse events will be monitored continuously
- Physical examination, haematology and serum biochemistry (Table 9-1) before treatment (Day 1) and during treatment on Day 15, Day 36, Day 50 and if surgery after week 10 (Day 64).
- TG02 treatment will be administered on Days 1, 8, 15, 22 and 36. If surgery after week 10 TG02 treatment will also be given at week 10 (Day 64).
- Pembrolizumab will be given on Days 22 and 36. If surgery is scheduled after Day 50/Week 8, pembrolizumab will be given at Day 50/Week 8. If surgery scheduled after Day 64/Week 10, a further pembrolizumab infusion will be given at Day 64/Week 10.
- DTH tests will be performed at baseline (Day 1), week 4 (Day 22), week 6 (Day 36) and week 8 (Day 50) (if surgery is scheduled for week 8 the DTH test should be performed two days before surgery). If surgery is after week 10, and the patient has had negative DTH tests up to and including week 8, an additional DTH test should be performed at week 10 (Day 64).

- Blood samples for in vitro assessment of TG02-specific immune responses (Immunology sample, PBMC) will be taken at baseline (Day 1) and Day 50. If surgery is after week 10, an additional sample should be taken as close as possible up to the date of surgery (see separate Immune monitoring plan).
- The CEA biomarker will be evaluated at Day 50. If surgery is after week 10 a third sample will be taken at Day 64 or just prior to surgery, whichever is the more appropriate.
- Tumour samples for assessment of immune response will be taken at time of surgery. If for any reason the patient will not have surgery a biopsy will be obtained if possible at the latest by week 14 (see separate Immune monitoring plan).
- FDG PET-CT scan for tumour assessment of standard uptake value (SUV-max) as close as possible up to date of surgery.
- Circulating Tumour Cells (CTC) will be evaluated at Day 1 and Day 50. If surgery is after week 10, an additional sample can be taken as close as possible up to the date of surgery.

Additional monitoring during the first 2 hours after any TG02-treatment:

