- d: Tumour tissue taken during resection. If for any reason, the patient will not have surgery a biopsy will be obtained if possible.
- e: To be done 2-0 days before surgery
- f: If surgery is scheduled for week 10, there will be no TG02-treatment given at week 10. If no surgery at week 10, the last TG02-treatment to be given at week 10.
- g: As close as possible up to the date of surgery.
- h: At the visits when TG02 and/or TG02-treatment (and pembrolizumab in Part II) is scheduled, the assessments should be performed prior to the treatments.
- i: Only to be taken for patients who have surgery after week 10 and had a negative DTH outcome at week 8. DTH (TG02) injection to be done 48 hours prior to surgery.
- j: Assessment of DTH (TG02) injection site to be done 48 hours (+/- 4 hours) after each DTH (TG02) injections by the patient in a study specific diary.
- k: Only applicable in Part II of the protocol
- l: To be done prior to surgery
- m: Allowed time for surgery (resection specimen) scheduled for week 8 is + 2 week and allowed time for surgery (resection specimen) scheduled for week 10 is + 4 week
- n: Blood samples for routine haematology and serum biochemistry to be recorded if already available in the patient medical record (standard of care)
- o: End of study visits to be scheduled during the hospitalized post-operative recovering period, up to 6 weeks after surgery.
- p: TG02-treatment is a combination of the two IMPs: GM-CSF and TG02. When TG02-treatment is administered, GM-CSF is to be given as an intradermal injection 15-30 minutes before the TG02 intradermal injection. GM-CSF and TG02 are administered as 2 separate intradermal injections, 15 to 30 minutes apart, at the same site in the upper arm. After any TG02-treatment the patients will be monitored for heart rate and blood pressure at 5, 10 and 30 minutes and then every 30 minutes thereafter for up to 2 hours post administration
- q: In addition, TG02 will, at certain time points, be administered intradermally (without prior administration of GM-CSF) in the lower area of the contra lateral arm as DTH test. The administration of GM-CSF (0.10 mL reconstituted GM-CSF) and TG02 (0.10 mL reconstituted TG02) has to be strictly intradermal.
- r: Should be within the last 4 weeks prior to first TG02-treatment.
- s: If surgery is scheduled after Day 50/Week 8, pembrolizumab will be given at Day 50/Week 8.

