- t: If surgery is scheduled after Day 64/Week 10, a further pembrolizumab infusion will be given at Day 64/Week 10.

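### Table 8-1 and the synopsis tie the week 8 pembrolizumab infusion to surgery on Days 51-63 and leave surgery on Day 64 or later uncovered, whereas Table 6-1, section 6.4.2 and Figure 3 tie it to any surgery scheduled after Day 50

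*Protocol*

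**What the plan says.** Two infusions are unconditional in Part II. Protocol section 6.4.2 states: "Pembrolizumab will be given on Days 22 and 36". The next two depend on the date of surgery, and the week 8 condition appears in two forms.

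- **Surgery on Days 51-63.** Table 8-1 footnote *** (section 8.2): "If surgery is taking place Day 51-63, pembrolizumab will be given at Day 50/Week 8". The synopsis (Duration of treatment, Part II) lists "week 8 if surgery takes place Day51-63/Week8-10, and week 10 if surgery is delayed after day 64/Week 10".
- **Any surgery after Day 50.** Table 6-1 footnote s (section 6.4.4): "If surgery is scheduled after Day 50/Week 8, pembrolizumab will be given at Day 50/Week 8". Section 6.4.2 and Figure 3 note 6 (section 6.2) give the same condition.

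For the week 10 infusion, Table 6-1 footnote t states: "If surgery is scheduled after Day 64/Week 10, a further pembrolizumab infusion will be given at Day 64/Week 10". The matching row of Table 8-1 is labelled "Week 10 (only if surgery is after week 10" and carries a pembrolizumab mark.

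On the total, section 8.2 states: "Dependent on time of surgery, a patient will receive pembrolizumab 2 to 4 times throughout the treatment period". Section 6.2 (Part II) gives a maximum of four infusions. Section 4.8 describes two-weekly dosing from week 4 up to surgery. The synopsis adds: "The dosing regimen should be the same for all patients at all sites".

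**The concern.** Section 8.2 is where pharmacy and nursing staff would look for the dosing rule, and Table 8-1 is the treatment schedule. Its footnote, like the synopsis, says nothing about the week 8 infusion when surgery falls on Day 64 or later. Those patients are expected: the surgery window runs to week 14, and Table 6-1 has separate columns for Day 64 and for Days 65-92. Staff working from Table 8-1 could reasonably conclude that a patient booked for, say, Day 70 does not receive the Day 50 infusion. Staff working from Table 6-1 would give it.

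Three things are at stake:

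- **Exposure before resection.** The resected tumour supplies the post-treatment sample for the change in intra-tumoural lymphocytes, a primary endpoint. Part II has at most 10 patients, so a few with different pembrolizumab exposure would matter to a descriptive summary.
- **The exposure summary.** SAP section 5.1 summarises the number of pembrolizumab administrations, the total dose, and the reasons for reduction, delay or discontinuation. Whether an absent Day 50 infusion counts as a departure depends on which rule is taken as the plan.
- **The per protocol set.** SAP section 4.4 has treatment deviations classed as major or minor, and SAP section 4.2 removes patients with major deviations from that set. With two conditions in the protocol, the same patient can be compliant under one and deviant under the other.

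**Working it through.** **Inputs.** Unconditional infusions: Days 22 and 36 (section 6.4.2). Conditional infusions: Day 50 and Day 64 (Tables 6-1 and 8-1). Dose: 200 mg per infusion (section 8.2). Let *d* be the day of surgery. Week 10 is taken as Day 64, as in Table 6-1 and section 6.4.2.

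**Table 6-1 rule.** N = 2 + [1 if d > 50] + [1 if d > 64].

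**Table 8-1 rule, with footnote *** read as restrictive.** N = 2 + [1 if 51 ≤ d ≤ 63] + [1 if d > 64].

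**The plan's own figure.** The Table 6-1 rule gives 2 for surgery up to Day 50, 3 for Days 51-64, and 4 from Day 65. That reproduces the stated range of 2 to 4. Under the restrictive Table 8-1 rule the two conditions can never both be met, so the maximum is 2 + 1 = 3 and the range is 2 to 3. On that reading section 8.2 conflicts with its own count, and with the maximum of four in section 6.2.

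| Surgery day | Table 6-1 | Table 8-1, restrictive reading | Difference |
|---|---|---|---|
| up to 50 | 2 (400 mg) | 2 (400 mg) | 0 |
| 51-63 | 3 (600 mg) | 3 (600 mg) | 0 |
| 64 | 3 (600 mg) | 2 (400 mg) | 200 mg |
| 65-92 | 4 (800 mg) | 3 (600 mg) | 200 mg |

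As a share of the Table 6-1 total, the difference is 200/600 = 33% for surgery on Day 64 and 200/800 = 25% for surgery on Days 65-92.

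**Interval.** For surgery on Day 65 or later, the restrictive reading gives infusions on Days 22, 36 and 64. The last gap is 64 − 36 = 28 days, against the two-weekly interval in section 4.8. Under Table 6-1 the days are 22, 36, 50 and 64, with every gap 14 days.

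**If footnote *** is not restrictive.** It is then silent for d ≥ 64. If the Day 50 infusion is supplied from the other passages, both tables give the same count on every day and the difference is zero.

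**Trigger wording.** Table 6-1 refers to surgery as scheduled, and Table 8-1 to surgery as it takes place. On Day 50 staff know only the schedule, and section 6.4 allows for postponement. The two conditions therefore differ in kind as well as in day range.

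**The case against.** The strongest reply is that the difference in counts needs a word that footnote *** does not contain. The footnote says *if*, not *only if*, whereas *only* does appear elsewhere in Table 8-1, in the week 10 row and in footnote **. On this view the footnote is incomplete for late surgery but does not withhold the infusion. The surrounding text supports that: section 8.2 and the synopsis both state a range reaching four, section 6.2 gives four as the maximum, Table 6-1 footnote t calls the Day 64 infusion a further one, and section 4.8 describes a two-weekly interval. All of this fits one cumulative schedule with a badly worded condition.

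This stands as an argument about intent. A reader might infer that the protocol sets out two regimens, or that patients with late surgery will receive 3 or 4 infusions according to the table used. The documents do not support that as a fact, because the counts of 3 and 2 hold only on the restrictive reading. A reader might also take the synopsis sentence on a common regimen as a demand for equal numbers of infusions. It is not one, since the same paragraph lets the number vary with the surgery date.

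The Day 64 comparison needs a further caveat. The synopsis labels Days 51-63 as weeks 8 to 10, while week 10 is Day 64 elsewhere, so that boundary is itself unclear.

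It is also fair to say that the SAP tests no hypothesis, lists every administration and lists deviations, so a divergence would be visible afterwards. That would not prevent it, nor settle which patients had deviated. The cumulative reading is reached only by using other passages to complete the dosing table, and for Day 64 neither conditional infusion in Table 8-1 is plainly triggered.

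**Conclusion.** The protocol is internally inconsistent on the condition for the week 8 pembrolizumab infusion: two places use Days 51-63 and three use any surgery after Day 50. Table 8-1 and the synopsis do not cover surgery on Day 64 or later. The possible consequence is one infusion (200 mg) per affected patient, and it rests on a restrictive reading of footnote *** and on week 10 meaning Day 64. On a cumulative reading there is no difference in dose, only an incomplete condition.

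This is most likely a drafting conflict. It touches only Part II patients with surgery on Day 64 or later, among at most 10, and the documents give no expected number. Nothing shows that a primary summary would become uninterpretable. It is nevertheless worth correcting: it sits in the dosing table, concerns a planned group of patients, and leaves compliance undefined for the exposure summary and the per protocol set. No view is taken here on which condition is right.

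**What to change.** Reconcile the following to one explicit condition for each infusion: the synopsis (Duration of treatment, Part II), Figure 3 note 6, section 6.4.2, Table 6-1 footnotes s and t, and Table 8-1 (footnote *** and the week 10 row). Each condition should:

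- state what happens when surgery is on Day 64 and when it is later;
- say whether it refers to the scheduled or the actual date of surgery;
- agree with the stated number of infusions and the interval in section 4.8, or have those statements changed to match.

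Which condition applies is for the sponsor to decide. The agreed rule should then be the reference for the pembrolizumab exposure summary in SAP section 5.1 and for classing treatment deviations under SAP section 4.4. The cost is protocol wording only: no added visits or data collection, and no change to the sample size.
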